6.9.2.2.3. Fusion success

Fusion will be assessed at 1 year, preferably by collecting a CT-scan, alternatively fusion may also be collected through X-Rays. If no fusion observed during the first fusion assessment, further fusion assessment(s) will be at the discretion of the investigator. The surgeon or hospital radiologist will determine fusion. Time-to-event analysis will be conducted for fusion success. The fusion success rate will be summarized at 1, 2, 3, 4 and 5-year follow-up, if applicable. If a subject shows fusion success at early timepoints and non-fusion at a later timepoint, the fusion status at all earlier points should be considered non-fusion. For 2-level subjects, fusion success will be defined as achieving fusion at both treated levels. In addition to the time-to-event analysis, the last evaluation for fusion will be summarized.

6.9.2.2.4. Secondary surgeries at index and/or adjacent level(s)

For secondary surgery at index levels and/or at adjacent levels, time-to-event (life table method) will be performed to estimate the cumulative event rate up to 5 years.

6.9.2.2.5. Adverse events

Detailed information about how AEs will be summarized can be found in section 6.10.

6.9.2.3. To observe and document the patients' short term recovery after surgery

The following analyses will be carried out for both primary and subgroup datasets defined in section 6.1.3.

6.9.2.3.1. Time needed for first ambulation

Time needed for first ambulation is defined as the days after the initial surgery for patients to get out of bed and ambulate with or without assistance. Summary statistic including mean, standard deviation, median, minimum and maximum for continuous variable will be provided.

6.9.2.3.2. Surgery recovery day

Surgery recovery day is defined as days after the initial surgery, when patients have no need for intravenous infusion of analgesic drugs, no ongoing surgery related AEs impending discharge, and no need for nursing care. Summary statistic including mean, standard deviation, median, minimum and maximum for continuous variable will be provided.

6.9.2.4. To document health resources consumption and perform economic analyses

Healthcare utilization will be measured with the following three cost components and summarized descriptively:

1. Resource: procedure, length of hospital stay, additional medical visit (outpatient consultation, visits to primary care services, etc.)
2. Medication: the number of patients who take pain medications at baseline and the past week before each followup visit will be summarized.
3. Non-pharmacologic therapies: the number of patients who utilize rehabilitation program between the scheduled followup visit and the previous scheduled visit will be summarized.

Economic analyses are not planned in this SAP.

6.9.2.5. To observe and document the patient profile when choosing a particular minimally invasive fusion procedure

The baseline information will be summarized by individual procedures.

6.9.3. Additional Analyses

1. Analyses for baseline information can be found in section 6.6.
2. Determine if there is a correlation between sagittal balance at baseline and the radiological findings (fusion) and the clinical outcomes at the follow-up visit, in those sites where this assessment is standard of care. Pearson correlation coefficient and 95% CI will be provided.
3. Hospital stay in days after the surgery when patients has been discharged from hospital will be summarized.
4. Days to first return to work will be summarized.
5. Sagittal balance parameters and change from the baseline if applicable will be summarized by visits in those sites where this assessment is part of standard of care. The parameters include pelvic incidence, sacral slope, pelvic tilt, and global lordosis angle.
6. Adjacent levels radiographic review will be summarized by visits if it is available. Instead of summarizing measurements of length of body and slip in millimeter, the percentage of slip or grade/type of spondylolisthesis, and disc relative height will be summarized due to zooming effect from x-ray and MRI.
7. Several subgroup analyses will be conducted based on Douleur Neuropathique 4 (DN4) scores (respectively for leg and back DN4 score) at baseline, 3-month and 12-month visit. Subgroups include:

This document is electronically controlled. Printed copies are considered uncontrolled.

Confidential

- Subjects with baseline $DN4 \geq 4$ and $DN4 \geq 4$ at 3-month follow-up
- Subjects with baseline $DN4 \geq 4$ and $DN4 < 4$ at 3-month follow-up
- Subjects with baseline $DN4 < 4$ and $DN4 \geq 4$ at 3-month follow-up
- Subjects with baseline $DN4 < 4$ and $DN4 < 4$ at 3-month follow-up
- Subjects with baseline $DN4 \geq 4$ and $DN4 \geq 4$ at 12-month follow-up
- Subjects with baseline $DN4 \geq 4$ and $DN4 < 4$ at 12-month follow-up
- Subjects with baseline $DN4 < 4$ and $DN4 \geq 4$ at 12-month follow-up
- Subjects with baseline $DN4 < 4$ and $DN4 < 4$ at 12-months follow-up

For each subgroup, the number and percentage of subjects will be provided. In addition, ODI, EQ-5D, VAS back and leg pain scores at baseline, at each follow-up and the improvement from baseline will be presented by the subgroups. Statistical comparison may be carried out for these subgroups analyses.

8. Regression analyses may be conducted by taking into consideration of pathology (spondylolisthesis versus non-spondylolisthesis) and surgical approach perspective (anterolateral versus posterior) to examine the influence of pathology or surgical approach on clinical outcomes including neurological status, $DN4$, EQ-5D and work status. Also analyses may be conducted to examine how the demographic information such as age predicts the clinical outcomes.

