**Days to first return to work**

Information on the days needed to first return to work will also be collected by the patient for the investigator in order to assess how long it takes for patients to return to work. Corresponding costs will be evaluated and included in the economic analyses.

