#### **G.1.3 Additional Data Analysis**

For other measurements, continuous variables will be summarized using mean, standard deviation, median, minimum and maximum while the categorical variables will be summarized using frequency and percentage.

Baseline information will be summarized for all DDD patients and by subgroups as outlined below and/or per surgical procedure (ALIF, OLIF, DLIF, PLIF, TLIF, MIDLF).

- 1) In DDD patients with spondylolisthesis and stenosis
- 2) In DDD patients with spondylolisthesis without stenosis
- 3) In DDD patients with stenosis without spondylolisthesis
- 4) All patients not included in subgroup 1), 2), 3).

Determining if there is a correlation between sagittal balance at baseline and the radiological findings and the clinical outcomes at the follow-up visit, in those sites where this assessment is standard of care.

Several subgroup analyses will be conducted based on DN4 scores (respectively for leg DN4 score and back DN4 score) at baseline, 3 months and 12-month visit. For subjects with baseline DN4  $\geq 4$ , the number and percentage of subjects with DN4  $\geq 4$  or  $< 4$  at 3 months and 12 months follow-up will be calculated and presented. Similarly for subjects with baseline DN4  $< 4$ , the number and percentage of subjects with DN4  $\geq 4$  or  $< 4$  at 3 months and 12 months follow-up will be calculated and presented.

In addition, ODI, EQ5D, VAS back and leg pain score at baseline, at each follow-up and the improvement of each variable from baseline at each follow-up will be presented by the subgroups defined by baseline DN4 scores and/or DN4 scores at follow-ups. Statistical comparison may be carried out for these subgroups.

More subgroups analyses may be conducted as exploratory analyses by taking into consideration of pathology and surgical approach perspective.

Any deviation(s) from the original statistical plan will be documented with a justification.

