6.2. General Methodology

In this study, the two-sided 95% CI will be conducted to test hypothesis for primary and the first secondary objectives. For other analyses without hypothesis testing, the analyses are descriptive in nature. In general, the categorical variables will be summarized using frequency tables and continuous variables will be summarized using mean, standard deviation, median, minimum and maximum.

Time-to-event (life table method) will be performed to estimate the cumulative event rate up to 5 years for secondary surgery at index levels or adjacent levels and AEs.

Time-to-event analysis will be conducted for fusion success.

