6.4. Handling of Missing Data and Dropouts

All data analyses will be based on the observed data. Missing data due to lost to follow-ups will not be imputed. For study subjects included in the primary analysis dataset who drop out or withdraw from the study, data collected before the occurrence of dropout or withdrawal will be included in analysis.

This document is electronically controlled. Printed copies are considered uncontrolled.

Confidential

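### The SAP does not say how patients who have not returned to work are counted, and under its default statistics they drop out, so return looks faster than it is

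*SAP*

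**What the plan says.** Protocol B.1.4 lists days to first return to work as an additional measurement, collected "in order to assess how long it takes for patients to return to work".

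The SAP gives it one line, 6.9.3 item 4: "Days to first return to work will be summarized". That line names no population, no denominator, no statistic and no rule for patients without a return date.

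Three general provisions fill the gap:

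- SAP 6.2: "continuous variables will be summarized using mean, standard deviation, median, minimum and maximum". Protocol G.1.3 has the same rule: "For other measurements, continuous variables will be summarized using mean, standard deviation, median, minimum and maximum while the categorical variables will be summarized using frequency". It adds percentages for the latter.
- SAP 6.4: "All data analyses will be based on the observed data".
- SAP 6.4 again: "Missing data due to lost to follow-ups will not be imputed".

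Time-to-event methods are reserved for other outcomes. SAP 6.2 uses the life-table method "to estimate the cumulative event rate up to 5 years for secondary surgery at index levels or adjacent levels and AEs", and adds that "Time-to-event analysis will be conducted for fusion success". Return to work is not on either list.

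Work status is scheduled at baseline, 4 weeks, 3 months and each year from 1 to 5 (Protocol E and E.7, assessment tables). In the SAP it appears at baseline (6.6) and as one outcome in an optional regression (6.9.3 item 8).

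**The concern.** Time to first return to work is a time-to-event outcome. At any data cut some patients will have returned, some will not have returned yet, some will never return, and some will have been lost or have died. Only the first group has a number of days.

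A mean or median of recorded days describes how quickly the returners returned. The Protocol asks how long patients take to return, which is a question about everyone who had a job to go back to. The two answers differ, and always in the same direction. A group in which few patients return, but those few return early, would look good on this summary.

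The blank field is also ambiguous. A patient who was retired before surgery and a patient who was working and never went back both have no return day, although the first does not belong in the denominator and the second does.

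**Working it through.** The documents give no return-to-work figure, so there is nothing to reproduce. The check is first a reading of the rules in sequence, then a short piece of algebra for the direction of the bias.

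**Applying the stated rules**

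1. Days to first return is a number, so SAP 6.2 and Protocol G.1.3 treat it as continuous: mean, standard deviation, median, minimum, maximum.
2. SAP 6.4 restricts analysis to observed values. A patient still off work has no observed value.
3. SAP 6.4 rules out imputation for loss to follow-up. Data collected before dropout are kept, but the time a patient spent off work without returning cannot enter a mean or median of return days.
4. No provision for censoring applies, because the SAP names time-to-event methods only for secondary surgery, AEs and fusion.

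The summary that results from steps 1 to 4 covers patients with a recorded return day and no others.

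**Direction of the bias**

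Let *r* be the share of patients working before surgery who have returned by the data cut. For simplicity, assume every patient is followed to that cut.

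- Half of the returners have returned by the returners-only median. As a fraction of all baseline workers that is *r* × 0.5. The reported median is therefore the *r*/2 quantile of the whole group, which is below the 0.5 quantile whenever *r* < 1.
- Conversely, the median for all baseline workers is the 0.5/*r* quantile of the returners' distribution.

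The shares below are assumptions, since the documents give none:

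| Assumed *r* | Returners-only median is this quantile of all baseline workers (*r*/2) | All-worker median is this quantile of the returners (0.5/*r*) |
|---|---|---|
| 0.90 | 0.45 | 0.56 |
| 0.75 | 0.375 | 0.67 |
| 0.60 | 0.30 | 0.83 |
| 0.50 | 0.25 | 1.00 |

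At *r* = 0.50 the all-worker median lies at the extreme end of the returners' distribution. Below that it is not reached, yet a returners-only median can still be printed.

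These are positions in a distribution, not days. Converting them to days needs the shape of the return-time distribution as well as *r*, and the documents give neither. They also do not say how many patients will be working at baseline.

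**The case against.** The strongest reply is that item 4 is silent rather than wrong. A reader might infer that the SAP plans to summarise returners only, but no sentence says so; that result comes from combining 6.2 with 6.4. This stands, and the point is worded accordingly. It does not remove the problem, because a programmer following the SAP as written would produce the returners-only table.

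Four stronger readings are tempting, and the documents do not support them:

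- **That patients who never return are hidden.** Work status is collected at every follow-up visit, and Protocol G.1.3 summarises categorical measurements by frequency and percentage, so non-returners could appear in a work-status table. The SAP does not commit to that table after baseline.
- **That the bias is known to be large.** Follow-up is 5 years. If nearly everyone eventually returned and stayed under observation, the final summary would be close to correct. Nor is the interim report limited to 3 months of data: it falls when all subjects have reached that visit, after about 4 years of enrolment, so only the most recently enrolled patients have such short follow-up.
- **That cost results would be distorted.** Protocol B.1.4 intends the variable for economic analyses, but SAP 6.9.2.4 says none are planned there, and return to work is not among its three cost components.
- **That a comparison of approaches would be misled.** Item 4 plans no such comparison. The split by approach in SAP 6.1.3 is attached to the primary endpoint and to the endpoints of secondary objectives 2 and 3.

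**Conclusion.** The point holds in a limited form. The SAP does not state how patients who have not returned to work are counted. Its default rules remove them, and the resulting summary is biased towards faster return. The direction follows from the algebra whenever some baseline workers have not returned. The size depends on the share who never return or are censored, and cannot be derived from the documents.

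This is more than a missing detail, because following the defaults gives a biased answer to the purpose stated in Protocol B.1.4, and the SAP already applies suitable methods to other outcomes. Severity is nevertheless low. The measure is additional and descriptive, carries no hypothesis test, and does not touch the primary conclusion.

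**What to change.** Replace SAP 6.9.3 item 4 with text that sets out:

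1. **Population:** patients working before surgery, including those on sick leave if the CRF records it. Give the number excluded as not working.
2. **Proportions:** number and percentage returned to work at each scheduled visit, with the number assessed as denominator.
3. **Time to return:** a Kaplan-Meier or cumulative incidence estimate of days from surgery to first return. Patients not returned are censored at last contact. Death, and retirement if recorded, are treated as competing events, which calls for cumulative incidence where they occur. Report the median, or state that it is not reached.
4. **Presentation:** overall and by approach (anterolateral, posterior), descriptively.

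The mean and median among returners may be kept if labelled as such and shown beside the number returned.

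The cost is SAP wording and one program using the return-to-work and work-status data already collected. The CRF is filed separately (Protocol K.2), so the sponsor should confirm that it captures sick leave, retirement and the date or day of return before the text is fixed.

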6.10. Safety Evaluation

The analyses include:

- Time-to-event (life table method) to assess the cumulative AE rate up to 4-week, 1-year, 2-year, 3-year, 4-year and 5-year visit intervals.
- Summary of number of AEs and number of subjects having AEs up to the 5-year visit.
 - All AEs
 - Serious Adverse Events (SAE)
 - Device related AEs
 - MAST™ Approach/Procedure related AEs
 - General Surgery related or Lumbar Fusion procedure related AEs
 - Disease related AEs.
 - Serious device related AEs
 - Serious MAST™ Approach/Procedure related AEs

A relatedness determination of "possible", "probable" or "causal relationship" is considered "related".

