#### **G.1.2 Analysis of Secondary Endpoints**

For the first secondary objective, the similar method as the one outlined above for the primary endpoint will be used to assess whether the ODI improvement at 3 months is equivalent for the non-spondylolisthesis DDD subjects treated with anterolateral approaches and the ones treated with posterior approaches.

For secondary points ODI improvement at other follow-ups other than at 3-months visit; change of VAS back and leg pain intensity and EQ-5D at all follow-ups through 5-year visit, summary statistics will be provided and the paired t-test will be used to test whether the improvement at each follow-up from baseline is significant.

The neurological success rate will be summarized at each follow-up. Overall neurological success will be defined as maintenance or improvement in all sections (motor, sensory, reflex, and straight leg raising) for the time period evaluated. In order for a section to be considered a success, each element in the section must remain the same or improve from the time of the baseline evaluation to the time period evaluated. Therefore, if any one element in any section does not stay the same or improve, then a patient will not be considered a success for neurological status.

Time-to-event-analysis will be conducted for fusion success. The fusion success rate will be summarized for 1, 2, 3, 4, 5-year follow-up, if applicable. If a subject shows fusion success at early timepoints and non-fusion at a later timepoint, the fusion status at all earlier time points should be considered as non-fusion.

For 2-level subjects, fusion success will be defined as achieving fusion at both treated levels.

For secondary surgery at index levels, secondary surgery at adjacent levels and AEs, survival analysis will be performed to estimate the cumulative event rate up to 5 years.

Healthcare utilization will be measured with the following three cost components:

- (1) resources: procedure, length of hospital stay, additional medical visits (outpatient consultations, visits to primary care services, etc)
- (2) medications and
- (3) non-pharmacologic therapies: rehabilitation program

For time needed for first ambulation and surgery recovery day, summary statistics for continuous variable will be provided by subgroups.

The analyses for the primary endpoint and secondary endpoints outlined in secondary objectives 2 and 3 will be done for all subjects and the following subgroups:

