6.1.3. Analysis Datasets

The primary analysis dataset defined in this study comprises of all subjects who are enrolled and receive a single or double level instrumented fusion using MAST™ minimally invasive PLIF, TLIF, DLIF, OLIF, ALIF and MIDLIF surgical procedures with a mandatory posterior fixation. For double levels instrumented fusion, the same procedure must be used for both levels. All the analyses will be carried out on the

This document is electronically controlled. Printed copies are considered uncontrolled.

Confidential

primary analysis dataset. For subjects who are enrolled but not included in the primary analysis dataset, their demographic and other baseline characteristics will be summarized separately. The reasons for not using minimally invasive procedure or surgery not done will be listed as well.

In addition to the primary analysis dataset, four subgroups are defined in the following:

- 1) DDD patients with spondylolisthesis and stenosis
- 2) DDD patients with spondylolisthesis but without stenosis
- 3) DDD patients with stenosis but without spondylolisthesis
- 4) All patients not included in subgroups 1), 2), 3).

The analysis for the primary endpoint and secondary endpoints outlined in secondary objectives 2 and 3 (section 4.2) will be performed on these four subgroups as well. For the primary analysis dataset and each of these four subgroups, the analysis will be carried out on further subgrouped by anterolateral and posterior groups.

Other subgroup analysis such as by number of treated levels may also be performed.

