6.8. Interim Analyses

In this study, in addition to final report, an interim report when all subjects reach 3-month visit is anticipated. The methodology described in section 6.2 will be used for the interim analyses. The cumulative event rate for secondary surgery at index levels or adjacent levels and AEs up to cut-off date of interim analyses will be conducted by time-to-event analysis (life table method).

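### SAP 6.10 lists serious and related adverse events only under counts of events and subjects; the planned life table should be stated to cover each of these categories

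*SAP*

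**What the plan says.** SAP 6.9.2.2.5 sends the reader to SAP 6.10 for how AEs are summarized, so 6.10 governs. It has two items.

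- The first allows for follow-up time: "Time-to-event (life table method) to assess the cumulative AE rate up to 4-week, 1-year, 2-year, 3-year, 4-year and 5-year visit intervals". It names no AE category.
- The second is a count: "Summary of number of AEs and number of subjects having AEs up to the 5-year visit". All eight categories sit under this item: all AEs, SAEs, device-related, MAST approach/procedure-related, general surgery or lumbar fusion-related, disease-related, and the serious forms of the device- and approach-related categories. No denominator, number at risk, person-time or interval is specified.

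The other passages on AEs also name no category. For secondary surgery and AEs together, Protocol G.1.2 says that "survival analysis will be performed to estimate the cumulative event rate up to 5 years". SAP 6.2 names the life-table method for the same purpose. SAP 6.8 applies it at the interim report to "The cumulative event rate for secondary surgery at index levels or adjacent levels and AEs up to cut-off date of interim analyses".

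AEs are an endpoint of secondary objective 2. Under SAP 6.1.3, for the full dataset and each pathology subgroup, "the analysis will be carried out on further subgrouped by anterolateral and posterior groups". For patients who leave early, SAP 6.4 says that "data collected before the occurrence of dropout or withdrawal will be included in analysis", with no imputation.

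**The concern.** Long-term safety is a stated aim, and Protocol A.1.1 justifies 5-year follow-up partly by rare adverse events. The categories that answer that aim are the serious, device-related and approach-related ones, and the method that allows for incomplete follow-up is not stated for them.

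The life table that is stated does not obviously fill the gap. Protocol B.1.3 has all AEs collected, including those that may have no direct link to the surgery. A curve for the first AE of any kind over 5 years therefore says little about, for example, device-related events.

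A patient lost at month 8 can show an event only during those 8 months. In a count over all treated patients, that patient weighs as much as one seen for 5 years. Events that can arise late are the most exposed. Protocol E.9.1.1 lists screw and rod breakage, cage migration, subsidence and degeneration of a previously healthy level.

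**Working it through.** **Inputs from the documents.** Follow-up is 5 years for every patient, and accrual takes about 4 years (Protocol B.8). The interim takes place when all subjects have reached 3 months (Protocol G.1.4, SAP 6.8). The documents state no AE rate, drop-out rate or safety precision, so there is no planned figure to reproduce.

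**Assumptions.** R is the true 5-year risk in a category, set at 20%. D is the drop-out by 5 years, set at 10% to 40%. Drop-out is unrelated to event risk.

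**1. Constant hazards, final analysis.** Let l = −ln(1−R)/5 and d = −ln(1−D)/5. The expected crude proportion over all treated patients is

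crude = l/(l+d) × [1 − (1−R)(1−D)].

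For R = 20%, l = 0.0446 per year. At D = 20%, d is also 0.0446, so crude = 0.5 × (1 − 0.8×0.8) = 18.0%. At D = 30%, d = 0.0713, so crude = 0.385 × (1 − 0.8×0.7) = 16.9%.

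| Drop-out by 5 years | Crude | Relative shortfall against 20% |
|---|---|---|
| 10% | 19.0% | 5% |
| 20% | 18.0% | 10% |
| 30% | 16.9% | 15% |
| 40% | 15.8% | 21% |

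The relative shortfall is nearly the same for R from 5% to 40%. Spreading drop-out evenly over the 5 years changes little: 18.1% at 20% drop-out and 17.1% at 30%.

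**2. Mostly perioperative events, final analysis.** Let 80% of the risk fall before any drop-out: 0.8 × 20% = 16%. The later risk among the remaining 84% is 1 − 0.80/0.84 = 4.76%. Then crude = 0.16 + 0.84 × crude(4.76%, D), which gives 19.8%, 19.6% and 19.4% at 10%, 20% and 30% drop-out. The relative shortfall is 1%, 2% and 3%.

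**3. By approach, final analysis, same true risk of 20%, constant hazard.** With 20% drop-out in both groups, the crude values are 18.0% and 18.0%, so there is no false difference. With 10% against 30%, they are 19.0% and 16.9%, a false difference of about 2 points.

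**4. Interim, no drop-out.** Assume even accrual over 4 years and a cut 3 months after the last enrolment. For follow-up spread evenly from a to b years,

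crude = 1 − [exp(−la) − exp(−lb)] / [l(b−a)].

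- All patients (0.25 to 4.25 years): 9.4%.
- First half of accrual (2.25 to 4.25 years): 13.5%.
- Second half of accrual (0.25 to 2.25 years): 5.4%.

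As an assumed contrast, let one approach enrol in years 0 to 3 and the other in years 1 to 4, with the same hazard. Follow-up is then 1.25 to 4.25 against 0.25 to 3.25 years, and the crude values are 11.5% and 7.4%.

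Now put 80% of the risk in the first 3 months. The later hazard is −ln(0.80/0.84)/4.75 = 0.0103 per year, over 1 to 4 against 0 to 3 further years. The crude values are 0.16 + 0.84×0.0253 = 18.1% and 0.16 + 0.84×0.0153 = 17.3%, a gap of about 0.8 points.

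**The case against.** The strongest reply is that the plan already allows for follow-up time. Four places plan a survival or life-table analysis of AEs, and none limits it to the first AE of any kind. SAP 6.10 introduces its list as what the analyses include, so silence on categories is not exclusion. This stands in part. That the categories receive counts alone is an inference from how 6.10 is laid out, and the sponsor may have meant more. But 6.10 is the governing section, and it does not say so.

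A reader might infer that the plan reports understated safety rates. The documents do not support that. SAP 6.10 specifies counts of events as well as subjects, not rates, and a count of observed events is not biased. The shortfall arises only if the count is divided by everyone treated and read as a 5-year risk. SAP 6.1.1 also provides an accountability table to read beside it.

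A reader might also infer that the two approaches are followed for different times and so cannot be compared. The documents do not say that either. Both have the same 5-year schedule, and the study aims to balance procedures (Protocol B.7). A procedure can close early in a region once its maximum is reached (Protocol B.5), so accrual timing could differ. That rule works by procedure and region, not by approach.

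On the interim, SAP 6.8 already names the life table for AEs, and no passage says that the category counts will be produced then. The 11.5% against 7.4% contrast rests on a one-year accrual shift that the documents do not state. Finally, these analyses are descriptive and approach is not randomized, so an approach difference in AEs would not be causal under either method.

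**Conclusion.** The point holds as a gap in SAP 6.10 with a cheap remedy, not as a finding that the safety results will be biased. The life table is stated only for an unqualified AE rate, while SAEs and the related-AE categories appear only under counts of events and subjects.

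How much this matters depends on when events occur. The 10% to 15% relative shortfall suits late device- or disease-related events better; the 1% to 3% suits dural tears, nerve root injury, hematoma or wound problems, most of which would be expected early. Both rest on assumed event and drop-out rates.

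A false approach difference at the final analysis needs unequal drop-out. At the interim it needs unequal drop-out or unequal enrolment timing, and there the range of follow-up, from about 3 months to over 4 years, leaves counts most open to misreading.

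**What to change.** In SAP 6.10, and by reference in 6.8, state that the planned life-table estimate applies to each listed AE category, overall and by approach. Define it as time from surgery to first event in the category, censored at last contact, with number at risk and 95% CI at each reporting time. Report events per patient-year beside the counts, so that repeat events are also set against follow-up. Keep the counts as supporting tables.

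The cost is a few sentences and a few more programmed tables. The estimates use the same kind of dates that the planned AE life table already needs. Intervals will be wide for rare categories, and the estimates still assume that drop-out is unrelated to event risk.
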